# 6.2.3.1 Treatment Group: Initial Treatment, Touch-up Treatment, and Follow-up

If the subject is randomized to the treatment group, treatment will be performed on the same day as randomization. In addition, vision assessments (Snellen visual acuity, confrontational visual fields, and ocular motility) will be performed before treatment. The EI will not be present during any of the treatment procedures.

Anesthesia will be administered following the standard practice at each investigational site. The application of ice and topical anesthesia is allowed to reduce injection discomfort. Injectable anesthesia must be limited to the treatment area insertion site only. The TI will use aseptic skin preparation and will administer injections according to the investigational directions for use (IDFU) and Section 9.1.2 of this protocol. The TI will determine the appropriate volume to inject to achieve at least a 1-grade improvement on the ALJDS based on clinical experience.

Approximately 30 minutes after treatment, the TI (or designee) will perform vision assessments. The TI will also evaluate treatment characteristics, including injection ease and product moldability, and will record any AEs.

Subjects will receive instructions on how to evaluate the treatment areas, assess the procedural pain on an 11-point scale, and complete the daily safety diary to record the presence or absence and severity of ISRs starting on the day of treatment and for up to 30 consecutive days after treatment. The diary is to be completed consecutively on a daily basis, until the subject returns for a touch-up/Month 1 Visit (as appropriate) or for 30 consecutive days, whichever is shorter.

Subjects will complete a safety follow-up telephone call 3 days after treatment. If any change to vision is reported during a telephone follow-up or unscheduled phone call, the subject will be asked to come in to the investigational site immediately or will be instructed to receive appropriate care, which may include referral to a retinal specialist. Subjects will return for an office visit 14 days after treatment to undergo 3D facial digital imaging, and the TI (or designee) will perform vision assessments. The subject will not see the blinded EI at the Day 14 visit.

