### **7.2** Safety Measures

Safety measures include:

- Subject assessment of procedural pain during treatment on an 11-point scale ranging from 0 (no pain) to 10 (worst pain imaginable)
- Subject assessment of jaw function using the 20-item Jaw Functional Limitation Scale questionnaire
- Presence, severity (mild, moderate, or severe), and days with ISRs recorded by subjects in daily safety diaries for approximately 30 consecutive days after any treatment (initial, touch-up, and maintenance)
- AEs observed by the TI or reported to the TI by the subject
- Snellen visual acuity, confrontational visual fields, and ocular motility assessed by the TI (or designee)
- EIs assessment of facial sensation
- Pronunciation video recordings
- Monitoring of concomitant medications and concurrent procedures

The subject daily diary will list the following ISRs that have been reported previously with HA dermal filler injections:

- redness
- pain after injection
- tenderness to touch
- firmness
- swelling
- lumps/bumps
- bruising
- itching
- discoloration

The subject's daily safety diary will list the following severities for ISRs to be recorded:

Subjects are to bring the e-diaries to their Day 14 and Day 30/Month 1 visits for review by the TI, and the TI will determine if the ISR qualifies as an AE.

AEs will be monitored continuously throughout the study and documented on an AE eCRF.

Vital sign measurements, including blood pressure (systolic and diastolic, while subject is seated), temperature, pulse, and respiratory rate, and a urine pregnancy test for female subjects of childbearing potential will also be performed. Females who are postmenopausal for at least 1 year or who do not have a uterus at the time of study entry are considered not of childbearing potential.

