### 8.3.3 Other Effectiveness Analyses

# 8.3.4 Safety Analyses

Subject assessment of procedural pain score and of jaw function using the 20-item Jaw Functional Limitation Scale questionnaire will be summarized descriptively. Assessments from the pronunciation recordings and facial sensation assessment will be summarized descriptively.

Snellen visual acuity, confrontational visual fields, and ocular motility assessments will be summarized descriptively.

ISRs will be summarized by maximum severity and ISR days for initial, touch-up, and maintenance treatments, separately. Summaries will include the incidence rate for each ISR.

Treatment-emergent AEs and treatment-related AEs (ie, device- or procedure-related) will be summarized by System Organ Class and Preferred Term, and severity. In addition, treatment-related AEs will also be tabulated by duration, severity, causality, action taken, and outcome. The summary will include incidence rate as well as total number of events.

AEs that occur after obtaining written IC but before treatment will be listed, but not summarized.

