5.6.4. Injection Site Responses

ISRs recorded in participant diaries after initial and touch-up treatments will be summarized for the VT population, and ISRs recorded after maintenance treatment will be summarized for the VMT population. The diary date and time will be compared with the treatment injection date and time to determine the corresponding treatment (ie, initial, touch-up, or maintenance) for each diary for the purposes of analysis. If there are multiple diary entries for any day, then the worse severity and maximum duration will be included in the summary for the corresponding symptoms analyzed. Descriptive statistics will be provided for the endpoints listed in [Table 5-10](#) for the initial treatment, touch-up treatment and maintenance treatment periods by predefined symptoms.

Table 5-10 **Injection Site Responses Analyses**

Endpoint	Description	Timing	Methodology
ISR severity	Maximum reported severity.	Initial, Touch-up, Maintenance	Categorical descriptive statistics
ISR duration	Duration from first instance of the symptom to the last instance of the symptom within the treatment period, where last instance means no further symptoms until the end of the 30-day diary period. Duration is derived as date of last ISR minus date of first ISR plus one, on the participant level, regardless of the side of the jaw.	Initial, Touch-up, Maintenance	Categorical descriptive statistics

Other symptoms of ISR entered in the e-diary by participants will be coded into medical terminologies by the medical safety physician. Other ISRs with “No,” “None,” or texts with a similar meaning will be coded as “N/A.” If other ISRs are coded as one of the prespecified symptoms (ie, redness, pain after injection, tenderness to touch, firmness, lumps/bumps, bruising, itching, and discoloration), then the participant will be counted only once based on the maximum severity and duration across the prespecified symptom entries and the coded terms. Other symptoms of ISR that are coded into terms beyond the list of prespecified symptoms will be summarized under “Other” symptoms in the summary tables for ISR. If a participant reported more than one non-prespecified terms of “Other ISR,” the participant will be counted once in the summary of “Other” symptoms for that treatment. The free texts entered by the participant, and the coded terms for “Other” symptoms will be included in the data listing.

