If the incidence of any particular category of “Other” ISR is greater than 5%, then the severity and duration analyses described in [Table 5-10](#) will be performed for that specific category of the “Other” ISR.

ISR day will be derived as ISR date – most recent treatment date + 1.

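### The SAP reports a first-to-last span for injection site responses where the protocol specifies days with the response, does not list the change, and does not mark symptoms still present at the last diary entry

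*SAP*

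**What the plan says.** Protocol 7.2 lists, among the safety measures, the presence and severity of ISRs and "days with ISRs recorded by subjects in daily safety diaries". Protocol 8.3.4 states the analysis: "ISRs will be summarized by maximum severity and ISR days for initial, touch-up, and maintenance treatments, separately". The synopsis says the same in both places.

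SAP 5.6.4, Table 5-10, has two ISR endpoints. One is maximum severity. The other is duration, measured from the first to the last instance of the symptom, "where last instance means no further symptoms until the end of the 30-day diary period". The formula is: "Duration is derived as date of last ISR minus date of first ISR plus one". The summary type is "Categorical descriptive statistics", with no cut-points given.

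The same section also defines a variable with a similar name: "ISR day will be derived as ISR date – most recent treatment date + 1".

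On when the diary stops, Protocol 6.2.3.1 has subjects complete it daily "until the subject returns for a touch-up/Month 1 Visit (as appropriate) or for 30 consecutive days, whichever is shorter". Footnotes to the schedule tables repeat this rule. In Protocol Table 2 the Day 30 visit has a window of -2/+10 days.

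**The concern.** Two separate gaps affect the ISR duration table.

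**The measure changed without being declared.** The natural reading of the protocol is a count of days on which the symptom was recorded. The SAP produces a calendar span. SAP 6.2.1 lists five changes to protocol-planned analyses, and this is not among them. Item 16 of the SAP version history (6.2.2) records a move to maximum duration, which does not tell a reader that a day count has become a span.

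**There is no rule for a symptom present at the last entry.** Its duration is computed like any other, and the SAP text provides no ongoing flag, censoring rule or reserved category.

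ISR duration is the subjects' own account of how long the device's common effects last. A participant with two brief episodes and one with a continuous symptom can be given the same duration, and a response that had not cleared looks the same as one that had.

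**Working it through.** The documents state no ISR-duration figure, so there is nothing to reproduce. The check applies both measures to the same diary patterns. The patterns are assumed for illustration and are not trial data.

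**Inputs**
- Protocol measure: C = number of diary days with the symptom recorded (7.2, 8.3.4).
- SAP measure: S = L - F + 1, where F and L are the first and last recorded days (Table 5-10).
- Diary stop: Day 30, or about Day 28 if the Day 30 visit falls at the early edge of its window (Protocol 6.2.3.1, Table 2).

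**Step 1. Does another SAP variable supply the count?** The SAP's ISR day is a date relative to the most recent treatment. It numbers a day; it does not count symptomatic days. No endpoint in Table 5-10 uses it. The protocol's measure is therefore not produced under 5.6.4.

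**Step 2. Span against count.** Every symptomatic day lies between F and L, so S is never smaller than C. S - C is the number of intervening days that were symptom-free or unrecorded.

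| Days recorded | C | S |
|---|---|---|
| 1 to 7, unbroken | 7 | 7 - 1 + 1 = 7 |
| 1 to 3 and 20 | 3 + 1 = 4 | 20 - 1 + 1 = 20 |
| Every other day, 1 to 29 | 15 | 29 - 1 + 1 = 29 |
| 1 and 25 only | 2 | 25 - 1 + 1 = 25 |

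Against the protocol's measure, the difference runs in one direction only.

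**Step 3. Symptom still present at the last entry.** Assume an unbroken symptom that truly lasts to Day 60.

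| Onset | Diary stops | S | C | True length |
|---|---|---|---|---|
| Day 1 | Day 30 | 30 - 1 + 1 = 30 | 30 | 60 |
| Day 1 | Day 28 | 28 - 1 + 1 = 28 | 28 | 60 |
| Day 10 | Day 30 | 30 - 10 + 1 = 21 | 21 | 60 - 10 + 1 = 51 |
| Day 25 | Day 30 | 30 - 25 + 1 = 6 | 6 | 60 - 25 + 1 = 36 |

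S and C are truncated identically, so the cause is the diary length combined with the missing rule, not the choice of a span. An open-ended top category would not catch the late-onset rows: 6 days would fall in a short-duration category.

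**Step 4. Wording of the diary end.** The SAP's definition of last instance assumes a 30-day diary, while the protocol lets the diary end earlier. The two need to agree before anyone can say which entry is the last.

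**Step 5. Missed entries.** SAP 5.6.4 gives no rule for unrecorded days. If a symptom lasts from Day 1 to Day 7 and the entries for Days 3 and 4 are missed, S = 7 - 1 + 1 = 7 and C = 7 - 2 = 5. Here the span is closer to the truth, so a day count needs missed days reported beside it.

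**The case against.** A reader might infer that reported durations are wrong in both directions, too long for intermittent symptoms and too short for persistent ones. The documents do not support that as a criticism of the span. Compared with the protocol's count, the span is never shorter. The truncation comes from the protocol's own diary stop rule, and returning to the count would not cure it.

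A reader might also infer that the SAP declares ongoing symptoms to have ended, or gives them the full diary length. It does neither. It is silent on ongoing symptoms, and the formula yields last entry minus onset plus one.

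Other points have weight:
- The protocol names days with ISRs but gives no derivation, and Protocol 8 leaves specifications to the SAP. A count is the natural reading, not a written rule.
- A span copes better with missed entries, as Step 5 shows.
- Table specifications are in a separate document, so an ongoing display there cannot be ruled out.
- Persistent responses have another route. The Treating Investigator reviews diaries and may record an ISR as an adverse event (Protocol 7.2), and treatment-related adverse events are summarized by duration without a 30-day limit (SAP 5.6.3, Table 5-9). This depends on the investigator's judgement, so it reduces the gap without closing it.
- ISR duration is descriptive; no test or success criterion depends on it.

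These points keep the matter small. They do not remove it: the SAP's stated rule gives a different number from the protocol's measure, the switch is undeclared, and the SAP text leaves truncated durations unmarked.

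**Conclusion.** The point holds as a minor one. SAP 5.6.4 replaces the protocol's days with ISRs by a first-to-last span, and SAP 6.2.1 does not say so. The two agree for an unbroken symptom and diverge otherwise (4 against 20 days in one illustrative pattern). Separately, a duration for a symptom present at the last entry is only a lower bound and is not identified as one (6 days for onset on Day 25 and a diary ending on Day 30).

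Neither effect can be sized, because the documents give no data on intermittent symptoms, missed entries or symptoms at diary end. The only indication is in Protocol 2.2: in the earlier study of this gel, the majority of ISRs had cleared within a week. If that carries over, truncation would affect a minority. The conclusion rests on reading days with ISRs as a count of recorded days and on the SAP text alone, without the separate table specifications. The primary endpoint is not affected.

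**What to change.** In SAP 5.6.4 and Table 5-10:
1. Add ISR days, derived for each symptom and treatment as the count of diary days with the symptom.
2. Keep the span as its own row, labelled as time from first to last occurrence.
3. Report the number and percentage of participants with the symptom on their last diary day as ongoing, with a note that their durations are lower bounds.
4. Report missed diary days beside the count, so that they are not silently read as symptom-free.
5. Replace the assumption of a 30-day diary with the protocol's stop rule, under which the diary may end earlier.
6. List any departure that is kept in SAP 6.2.1.

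The cost is one extra derivation and two extra rows per symptom, all from diary data already collected. The drawback is that missed entries can bias a day count downward, which is why item 4 is needed and why the span is worth keeping beside it.

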#### 2.2 Risk and Benefit

HA skin injection procedures carry the usual risks of erythema, pain, tenderness, swelling, itching, bleeding, bruising, lumps/bumps, firmness (induration), and skin infection. Allergic reactions to anesthetic agents are rare and may include skin rash, redness, itching, hives, burning, stinging, swelling, tenderness, and transient (temporary) loss of skin color.

Results of a multicenter, single-blind, randomized, controlled clinical study (V25L-001) conducted in 120 subjects demonstrated that VOLUX XC injectable gel was safe and effective in restoring and creating facial volume, and in sculpting, shaping, and contouring in the chin and jaw area. The primary effectiveness measure (glabella, subnasale, and pogonion angle measured by the blinded image-analysis technician from digital images of the subject's facial profile) showed significant improvement in projection of the chin. Procedural pain in this study was minimal. The most common injection site responses (ISRs) after initial/touch-up treatment were firmness, tenderness to touch, and swelling, and most ISRs resolved within 1 week of treatment. Prior to repeat treatment, treatment-related adverse events (AEs) were observed for 38.7% of subjects treated with VYC-25L injectable gel, with the most common being mild injection site mass (verbatim term: lumps/bumps). These are commonly reported events following treatment with HA dermal fillers. Most treatment-related AEs did not require treatment. A small percentage of treated subjects (3.4%, 4/119) after initial or touch-up treatment and 1.1% (1/89) after repeat treatment experienced

treatment-related AEs of speech disorder (investigator term: unclear pronunciation), considered to be related to the physical presence of filler in subjects' chin. The events were mild in severity, self-limiting, and resolved without sequelae within a few days. The subjects who experienced these events tended to have larger than average volumes injected into the pogonion and mentum (> 1.5 mL in each area). No deaths or treatment-related serious adverse events (SAEs) were observed.

The results of Study V25L-001 demonstrate that treatment with VOLUX XC injectable gel is an effective treatment for restoring and creating facial volume. The safety profile indicates that VOLUX XC injectable gel is safe and well tolerated by subjects in all treated areas.

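### SAP 5.6.4 leaves swelling off its list of prespecified injection site responses, so free text coded as swelling would not be merged with the diary swelling item

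*SAP*

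**What the plan says.** **Protocol, section 7.2 (Safety Measures).** "The subject daily diary will list the following ISRs that have been reported previously with HA dermal filler injections". Nine symptoms follow, and swelling is the fifth.

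**Protocol, section 2.2 (Risk and Benefit), on study V25L-001.** "The most common injection site responses (ISRs) after initial/touch-up treatment were firmness, tenderness to touch, and swelling".

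**Protocol, section 8.3.4 (Safety Analyses).** The ISR summaries are to give an incidence rate for every ISR.

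**SAP, section 5.6.4 (Injection Site Responses).** Diary ISRs are summarized "for the initial treatment, touch-up treatment and maintenance treatment periods by predefined symptoms". A separate rule covers what participants type in as other symptoms, which the medical safety physician codes:

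- The prespecified symptoms are given as "redness, pain after injection, tenderness to touch, firmness, lumps/bumps, bruising, itching, and discoloration". Free text coded to one of these is merged with the diary entries for that symptom, with one count per participant at the worst severity and longest duration found in either source.
- Free text coded to anything outside that list goes into a row labelled 'Other'. A participant with several such terms counts once there, and the free texts and coded terms are listed.
- A category of 'Other' with incidence above 5% gets its own severity and duration analysis.

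**SAP, section 6.2.** The changes to protocol-planned analyses (6.2.1) do not mention removing swelling. Item 16 of the version history (6.2.2) says that the analysis of other symptoms by coded term came in with version 2, and it mentions no removal either.

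**The concern.** The eight-item list is part of an operating rule. It separates free text that is merged with a diary symptom from free text that is set aside under 'Other'. With swelling off the list, a programmer who follows the text would treat it differently from the other eight diary symptoms, with no reason given.

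At stake is the swelling row of the ISR table: how many participants had swelling, how severe it was at worst and how long it lasted. The earlier study gives reason to expect swelling to be common. The ISR table is descriptive, and no effectiveness endpoint or hypothesis test depends on it.

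**Working it through.** The plan states no figure to reproduce here. The check compares the two lists, traces the rule, and then bounds the possible effect.

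**1. The lists side by side**

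| Protocol 7.2 diary | SAP 5.6.4 list |
|---|---|
| redness | present |
| pain after injection | present |
| tenderness to touch | present |
| firmness | present |
| swelling | **absent** |
| lumps/bumps | present |
| bruising | present |
| itching | present |
| discoloration | present |

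The protocol has 9 items and the SAP has 8, so 9 − 8 = 1 is missing. The SAP adds none. The order and names otherwise agree.

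**2. What the rule does to swelling reports**

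- *Diary item only.* The free-text rule is not used, so nothing is lost.
- *Free text only.* The coded term is not on the list, so the participant goes to 'Other' and is missing from the swelling row.
- *Both.* The participant stays in the swelling row and also appears under 'Other'. The swelling row understates severity or duration only if the free-text entries are worse or extend the episode.

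Example for duration, which SAP Table 5-10 defines as last date minus first date plus one: diary swelling on days 1 to 5 and free-text swelling on day 12. Unmerged, the swelling row shows 5 − 1 + 1 = 5 days. If the entries are pooled, it shows 12 − 1 + 1 = 12 days. If the merge rule instead means the larger of two separately computed durations, the result is max(5, 12 − 12 + 1) = 5 days, and this example shows no loss.

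**3. Possible loss of incidence**

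Let p be the true proportion with swelling and f the share of those who report it only as free text. The swelling row shows p × (1 − f), so the loss is p × f. The documents give neither p nor f; both ranges are assumptions. Loss in percentage points:

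| f | p = 30% | p = 60% | p = 90% |
|---|---|---|---|
| 0 | 0 | 0 | 0 |
| 1% | 0.3 | 0.6 | 0.9 |
| 5% | 1.5 | 3.0 | 4.5 |
| 10% | 3.0 | 6.0 | 9.0 |

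**4. What the 5% rule catches**

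SAP section 3 expects at least 176 treated. Using 176 as the denominator, 0.05 × 176 = 8.8. Eight participants with free-text swelling (8/176 = 4.5%) stay in pooled 'Other'; nine (9/176 = 5.1%) trigger a separate analysis. In the table above, free-text-only reporters alone exceed 5% in just two cells (6.0 and 9.0). Participants who report both ways also count towards the threshold, so it could be reached sooner. Even then the result is a second swelling analysis next to the diary one; the two are not merged.

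**5. After the correction**

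With swelling on the list, both documents have nine symptoms, free text coded as swelling is merged, and the loss p × f is 0.

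**The case against.** The strongest reply is that the omission hardly matters in practice. Swelling is a diary item in its own right, and the eight-item list appears only in the free-text rule, so a participant who marks swelling in the diary never meets it. Few people would leave that item blank and type the same word elsewhere. The 5% rule, the listing of coded terms, and the treating investigator's review of the diaries (protocol 7.2) keep stray reports visible. Since the lists otherwise match and no removal is recorded, the omission looks like a drafting slip.

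Most of this stands, and it limits the point to a minor one. It does not remove the point: the rule as written still treats swelling unlike the other eight symptoms, and none of the safeguards puts a free-text report back in the swelling row.

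A reader might infer two stronger conclusions, and the documents support neither:

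- *Swelling will be under-counted.* This needs participants who report swelling only as free text. The documents do not say how many there will be, and there may be none.
- *Swelling will have no row in the ISR tables.* The SAP spells out the predefined symptoms nowhere else, so this reading is possible. But the table specifications are in a separate document that is not available here, protocol 8.3.4 requires an incidence rate for each ISR, and SAP 6.2.1 declares no departure from that. This is a reason to make the SAP explicit. It is not evidence that the row is missing.

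**Conclusion.** Wrong as written; minor. That the SAP list conflicts with the protocol diary is certain. That the free-text rule, followed literally, sends coded swelling to 'Other' is also certain.

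The numerical effect is uncertain and probably small. It could slightly understate swelling's incidence, maximum severity or duration, and it is zero if nobody reports swelling as free text. The percentages under the working rest on assumed values of p and f and on 176 as the denominator, and they show scale only. The judgement that the effect is small rests on most swelling reports coming through the diary item.

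**What to change.** In SAP 5.6.4, insert swelling in the prespecified list between firmness and lumps/bumps, or replace the list with a reference to the diary list in protocol 7.2. Add one sentence stating that the tables by predefined symptom cover all nine diary items. Check that the separate table specifications agree.

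The cost is one word and one sentence. No data collection, sample size or effectiveness analysis changes.
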